8.2 Safety Endpoints

They include:

- changes from baseline in creatinine;
- vital signs;
- laboratory values including liver function tests, rate of aquaretic AEs, thus including serum sodium, rate of Metformin Associated Lactic Acidosis, blood insulin and glucose levels, HOMA test in both treatment groups.

9. VISITS

9.1 Trial Procedures

9.1.1 Screening:

After written informed consent has been signed, assessments during the screening visits will include:

1) Confirm diagnosis and determine whether the subject meets inclusion and exclusion criteria and record demographic information;

- 2) Perform physical examination, including post-void body weight and height (first visit);
- 3) Record medical/PKD history (all visits);

4) Record concomitant medications and ensure subject's treatment meets current standard of care including lifestyle and dietary recommendations, especially for ingestion of at least
2-3 liters of fluid per day as appropriate, unless otherwise directed by study doctor (all visits);

5) Assess AEs, if reported (all visits);

6) Assess vital signs (include heart rate and blood pressure) (all visits);

7) Serum pregnancy test for WOCBP (1st visit);

8) Collect urine and blood samples for clinical laboratory analyses, including serum creatinine, liver function tests, glucose metabolism parameter, CBC and venous gas analysis (1st, 2nd visit);

9) Non contrast enhanced CT-scan of the kidneys for TKV measurement (3rd visit, once eligibility has been confirmed). In case a patient has undergone kidney CT- or MRI-scan in order to measure TKV within 6 months before randomization, basal CT scan for TKV measurement may be not undertaken).

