Once the appropriate essential information has been provided to the subject and fully explained in layman's language by the investigator (or a qualified designee) and it is felt that the subject understands the implications of participating, the IRB/IEC-approved written ICF shall be personally signed and dated by both the subject and the person obtaining consent (investigator or designee), and by any other parties required by the IRB/IEC. The subject shall be given a copy of the signed ICF; the original shall be kept on file by the investigator. All of the above mentioned activities must be completed prior to the subject's participating in the trial. Every phase of the trial will be conducted in compliance with the protocol, GCP and the applicable regulatory requirement.

The trial contemplates a **2 weeks screening period** (included in a 9 months total recruitment period) during which 3 visits have to be collected (the 1st and the 2nd in three days, and the 3rd after biochemical analyses performed during the first two visits have been reviewed). The subject's eligibility for the trial will be confirmed by the mean of eGFR calculated from the 2 pre-treatment, central-lab, serum creatinine assessments. Longer screening periods (up to 4 additional weeks) are acceptable for subjects needing stabilization after changing or discontinuing other treatments, especially anti-hypertensives and diuretics. In this case Subjects must sign ICF and then agree to be switched to an alternate form of therapy in order to be eligible. As part of this stabilization or wash-out period different lab safety tests may be performed. Subjects who fail to meet trial requirements during the screening period may be rescreened at a later date.

Once eligibility is assessed, patients will undergo non-contrast enhanced CT-scan of kidneys (if not performed within six months prior to randomization).

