4.1 Screening Period (up to Day -30)

No investigational treatments will be administered during the screening period.

Preliminary eligibility for the trial will be initially assessed using the subjects' historical laboratory or imaging data.

During this period, the subject's eligibility for the trial will be confirmed using historical genetic test data and imaging data of the kidneys to support a diagnosis of ADPKD and to verify the level of CKD primarily due to ADPKD and not to other renal (hypoplasia) or metabolic (diabetic or hypertensive nephropathy) disorders.

Eligibility will be confirmed by the mean of eGFR calculated from the subjects' 2 pretreatment, central-lab, serum creatinine assessments (collected at least 24 hours apart). The final screening visit on Day -29 will not be scheduled until laboratory results from the second screening visit (V2) are received and evaluated. The eGFR values will be estimated based on the Chronic Kidney Disease-Epidemiology (CKD-EPI) formula. Subjects will be told that they will receive tolvaptan or metformin during the subsequent periods of the trial.

On Day -30, patients will undergo TKV measurement by means of Ct- or MRI-scan (if not already performed within the 6 months before the enrollment). Then, patients will be randomized to receive either metformin or tolvaptan and they will be told to start IMP assumption since the day after randomization.

Those randomized in metfromin arm will receive Zuglimet® 500 mg (2 packages, each of them containing 3 blisters; every blister contains ten 500 mg coated tablets).

Those randomized to tolvaptan arm will receive Jinarc® 45/15 mg (2 packages, each of them containing 4 blisters; every blister contains seven 15 mg tablets of and seven 45 mg tablets).

The screening period will last 1-2 weeks, but may be extended up to an additional 8 weeks for subjects who require modification of medical care or further medical evaluation specifically for this trial. This may include, for example, stabilizing anti-hypertensive regimens for subjects discontinuing diuretics or "wash-out" of other investigational agents.

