8.1.2 Secondary Endpoints

The key secondary endpoint is *the percent change from baseline in htTKV as measured by CT-scan at 24 months*. The use of htTKV as a surrogate biomarker for progression of ADPKD is supported by the Consortium for Radiologic Imaging Study of Polycystic Kidney Disease (CRISP) which showed that baseline TKV strongly predicts subsequent loss of GFR. TKV is now widely used in RCTs for ADPKD.

Other secondary efficacy end-points include:

- Difference in rate of albuminuria change;

- Difference in rate of urological events and of hypertension onset (for not hypertensive patients at baseline);
- Hypertension worsening or amelioration (for those who are hypertensive);
- Exploratory efficacy Outcomes (changes from baseline in urinary EGF and EGF/MCP-1 levels).

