9.1.4 Treatment Period

Assessment at each on-treatment visit will include:

1) Perform physical examination, including post-void body weight and height;

2) Record medical/PKD history;

3) Record concomitant medications and ensure subject's treatment meets current standard of care including lifestyle and dietary recommendations, especially for ingestion of at least2-3 liters of fluid per day as appropriate, unless otherwise directed by study doctor;

4) Assess AEs, if reported;

5) Assess vital signs (include heart rate and blood pressure);

6) Serum pregnancy test for WOCBP;

7) Collect urine and blood samples for clinical laboratory analyses, including serum creatinine, liver function tests, glucose metabolism parameter, CBC and venous gas analysis;

8) IMP dispensation;

9) IMP reconciliation (subjects must return any unused IMP);

10) Non contrast enhanced CT-scan of the kidneys for TKV measurement (at the end of month 24).

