9.1.6.2 TKV measurement

Abdomen-pelvis CT-scan will be performed by using a 320-row multi detector device and the following acquisition parameters will be used: slice thickness 0.5 mm, increment 0.5 mm, rotation time 0.5 s; 120/200 kVp/mAs.

An automatic dose modulation system will be used in all cases. Images will be acquired without intravenous injection of iodinate contrast material. Scans will be performed from the diaphragm to the pubic symphysis.

CT data will be centrally transferred to and analysed on a workstation (HPXW8600), present within the DETO equipped with software dedicated to image reconstruction (Vitrea FX 2.1, Vital Images, Minneapolis, MN, USA). For each patient, Multi-planar Reconstructions (MPR) on the axial, coronal and sagittal planes and Volume Rendering

(VR) images will be used in order to assess renal parenchyma. A radiologist with more than 10-year experience in the field of abdominal CT will manually trace both kidneys (renal parenchyma and all cysts including exophytic cysts), excluding the renal pelvis and other hilar vascular structures. The semi-automatic 3D Analysis software will be used in order to quantify the TKV for each CT examination. All changes in TKV (delta TKV) will be calculated by analyzing any variation of absolute TKV values deriving from the different CT examinations.

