12.3 Statistical Methods

A comparative analysis for the primary outcome will be carried out under the principle of "intention-to-treat" and including data from all subjects who are randomized. The efficacy and safety of compared interventions will be assessed. Trial data will be summarized by the calculation of means and standard deviations for normally distributed variables, medians and interquartile ranges for non-normally distributed variables, and frequency and percentage for categorical variables. Missing data will be ignored. The primary and secondary outcomes, namely the slope of the annualized eGFR and TKV will be analyzed using standard statistics including linear mixed-effects models. A P value <0.05 will be deemed significant.There are no plans for interim analyses.

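### Key secondary htTKV endpoint: change is defined by CT, yet the baseline may be an MRI and up to six months old, and section 12.3 handles neither modality nor scan date

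*Combined protocol and SAP*

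**What the plan says.** Section 8.1.2 names as key secondary endpoint "the percent change from baseline in htTKV as measured by CT-scan at 24 months". Sections 4 and 9.1.4 make the Month 24 scan a CT. Section 9.1.6.2 gives acquisition settings and a central reading method for CT only, and says that TKV change "will be calculated by analyzing any variation of absolute TKV values deriving from the different CT examinations".

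The baseline scan has three rules:

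- **Synopsis and section 4:** CT only. Once eligible, "patients will undergo non-contrast enhanced CT-scan of kidneys (if not performed within six months prior to randomization". Figure 1 also lists only CT, at the second screening visit and Month 24.
- **Section 4.1:** either modality, even for a new scan on Day -30: "TKV measurement by means of Ct- or MRI-scan (if not already performed within the 6 months before the enrollment". This is the only place where the window is counted from enrolment.
- **Section 9.1.1, item 9:** a new scan is CT, but where there has been a "CT- or MRI-scan in order to measure TKV within 6 months before randomization, basal CT scan for TKV measurement may be not undertaken".

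On analysis, section 12.3 covers the primary and secondary outcomes together, "namely the slope of the annualized eGFR and TKV will be analyzed using standard statistics including linear mixed-effects models". It adds "Missing data will be ignored". It mentions neither scan modality nor scan date.

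**The concern.** The endpoint is a CT-to-CT change over a nominal 24 months, but the baseline rules admit another modality and scans of different ages. A site can follow section 4.1 or 9.1.1 correctly and supply a baseline for which section 9.1.6.2 describes no reading method. No section says outright that a permitted MRI is the baseline value.

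An older baseline scan adds growth from before randomisation to the measured change. An MRI baseline adds any systematic difference between the two methods. Both add variance to the arm comparison and shift the reported within-arm change away from a 24-month figure.

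Section 12.3 does not settle this. Its wording suggests an annualised TKV slope, while section 8.1.2 asks for percent change. If the slope used actual scan dates it would absorb scan interval, but the section does not say so, and nothing there deals with modality. Two analysts could follow the plan and report different measures.

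**Working it through.** **Inputs from the documents.** TKV growth averages 5-6% per year (section 3.1). A trial month is 28 days (section 7.1), so Month 24 is Day 24 x 28 = 672. Randomisation is on Day -29 (section 4; the heading of 4.2 says Day -30, which changes the long interval by one day). A new scan is on Day -30 (section 4.1). Six months is taken as 183 days.

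**Scan-to-Month-24 interval**

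- New scan: 30 + 672 = 702 days = 1.922 years.
- Oldest permitted scan, counted from randomisation: 183 + 29 + 672 = 884 days = 2.420 years.

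**Expected change for one patient**, (1 + g)^years - 1:

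| Interval | g = 5% | g = 6% |
|---|---|---|
| 702 days | 9.83% | 11.85% |
| 884 days | 12.53% | 15.15% |
| Gap | 2.70 points | 3.30 points |

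**If section 12.3 means an annualised rate.** Dividing by a nominal 2 years gives 4.9-5.9% per year for the new scan and 6.3-7.6% for the oldest. Dividing the log change by the actual interval makes the two agree, but it dilutes the treatment contrast, because growth before the first dose does not depend on arm. Treatment runs from Day -28 to Day 672, 700 days, so the contrast keeps 700/884 = 79% for the oldest scans and 700/702, nearly all, for new ones.

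**Modality (assumption; the documents give no figure).** If MRI reads 2-5% below CT, a true change of 9.8% appears as 12.1-15.6%. If it reads 2-5% above, the same change appears as 7.7-4.6%.

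**Effect on power (illustration).** The documents give no SD for htTKV change, no MRI share and no distribution of scan ages. Assume an SD of log change of 0.06, a comparison with 80% power when all baselines are new CTs, and growth of 5.5% per year. The shift from a six-month-old scan is a = (182/365.25) x ln 1.055 = 0.0267. With inflated variance, power = Phi(2.802 / sqrt(1 + added share) - 1.960).

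- Ages spread evenly over 0-6 months, no MRI: a^2/12 adds 1.7% to the variance; power 79.4%.
- Half new, half exactly six months old, no MRI: a^2/4 adds 4.9%; power 78.1%.
- The half/half split with MRI share q, all MRIs among the old scans, and offset b: added variance = a^2/4 + b^2 q(1-q) +/- 2ab q x 0.5, plus if MRI reads low and minus if it reads high.
  - q = 0.1, b = ln 1.02: +7.4% or +4.5%; power 77.1% or 78.3%.
  - q = 0.3, b = ln 1.05: +29.7% or +8.0%; power 69.2% or 76.9%.

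**What covariates recover (simulation, assumed inputs).** The simulation used 3,000 runs, 75 per arm, growth SD 2.5 points per year, reading error 2%, half of baselines 0-183 days old, 60% of those MRI, and a true difference of 0.016 log units per year. Adding scan interval and modality moved power from 80.7% to 87.8% with a 5% offset and MRI reading low. With no offset it moved from 88.6% to 89.0%. Rejection with no true effect stayed at 4.8-5.8%. Dividing by the full scan interval gave an estimate about 6% too small.

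**The case against.** **MRI patients are not clearly without an endpoint.** A reader might infer from section 9.1.6.2 that a patient with only an MRI baseline has no change value and leaves the analysis because missing data are ignored. If 10-30% were lost in this way, 80% power would fall to 76-65%. The documents do not support that as the likely course. Section 4.1 provides for measuring TKV by either modality, and section 9.1.1 waives the CT only when the earlier scan was done to measure TKV. The natural reading is that the permitted MRI is the baseline. What stands is that no section says so and none describes how to read it.

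**The window conflict is narrow.** The synopsis, section 4 and section 9.1.1 all count from randomisation; only section 4.1 says enrolment. Section 10.1.11 uses enrolment for a point after the pregnancy test, which is close to randomisation. Only if the word meant the start of a 2 + 8 week screening would the interval reach 183 + 70 + 29 + 672 = 954 days (13.6-16.4%).

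**Central reading is largely covered.** Section 9.1.6.2 sends CT data for central analysis, and an earlier CT used as baseline would reasonably fall under that. The gap is confined to MRI scans and to earlier CTs not acquired to the stated settings.

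**The power loss is mostly assumption.** The 69% figure needs 30% MRI, a 5% offset, MRI reading low and every MRI being an old scan. The 79% contrast applies only to the oldest scans under an annualised analysis. Neither describes the expected loss.

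**Bias between arms** is a tempting inference in an open-label trial. Sections 4 and 4.1 place the scan before 1:1 randomisation, so its age and modality differ between arms only by chance. Section 4.2 lets the scan and randomisation fall on the same visit, so the order should be stated, but nothing there puts the scan after allocation.

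**The plan's mixed model is not wrong.** Fitted to log htTKV on actual scan dates with a modality term, it would serve as well as ANCOVA.

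**Conclusion.** The point holds in limited form. The baseline rules contradict each other on modality. Section 12.3 neither matches the percent-change endpoint nor deals with modality or scan date.

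From the documents' own figures, permitted scan age alone moves one patient's expected change by 2.7-3.3 points on a base of about 10-12%. MRI adds an offset that the documents do not size.

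The harm is lost precision and a within-arm change that is not a clean 24-month figure. Scan age alone costs under about 2 points of power on the assumptions shown. The loss becomes material only if MRI baselines are common and the offset between methods is several percent; the documents show neither. The concern is confined to the key secondary endpoint and is a change worth making, not one that threatens the trial.

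**What to change.** 1. Reconcile the synopsis, sections 4, 4.1, 9.1.1 and 9.1.6.2, and Figure 1 on baseline modality. State whether a permitted MRI is the baseline value. If it is, add a reading method for MRI, and say how an earlier CT outside the section 9.1.6.2 settings is treated.
2. Use randomisation as the single anchor for the six-month window, and state that the baseline scan is fixed before the patient is registered for allocation.
3. Record the date and modality of every baseline scan.
4. In section 12.3, analyse ln(htTKV at Month 24 / htTKV at baseline), back-transformed to percent to match section 8.1.2. Include treatment, ln(baseline htTKV), scan-to-randomisation interval and, if MRI stays allowed, modality. Use ANCOVA, or an equivalent mixed model on actual scan dates.
5. Add a sensitivity analysis limited to CT-CT pairs.
6. If an annualised rate is also reported, use actual dates and note the dilution from growth before randomisation.

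**Cost.** Protocol and SAP wording, two recorded fields and up to two degrees of freedom out of about 150 patients. The modality term will be imprecise if few baselines are MRI, and the covariates remove only average effects. ANCOVA on change omits patients without a Month 24 scan; a mixed model keeps them but gains little about change from a single scan. If MRI baselines are ruled out, patients with only an MRI would need a baseline CT.

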9.1.2 Randomization

Assessments during the randomization visit will include:

1) Verification of diagnosis, inclusion and exclusion criteria and record demographic information;

2) Record medical/PKD history;

3) Record concomitant medications and ensure subject's treatment meets current standard of care including lifestyle and dietary recommendations, especially for ingestion of at least2-3 liters of fluid per day as appropriate, unless otherwise directed by study doctor;

4) Assess AEs, if reported;

5) Assess vital signs (include heart rate and blood pressure);

6) IMP dispensation;

9.1.3 Titration period

Assessments during up-titration phone call will include:

1) Assess IMP tolerability;

2) Assess AEs, if reported.

9.1.3 Run-in Period

Assessment at the end of run-in period visit will include:

1) Perform physical examination, including post-void body weight and height;

2) Record medical/PKD history;

3) Record concomitant medications and ensure subject's treatment meets current standard

of care including lifestyle and dietary recommendations, especially for ingestion of at least

2-3 liters of fluid per day as appropriate, unless otherwise directed by study doctor;

4) Assess AEs, if reported.

5) Assess vital signs (include heart rate and blood pressure);

6) Serum pregnancy test for WOCBP;

7) Collect urine and blood samples for clinical laboratory analyses, including serum creatinine, liver function tests, glucose metabolism parameter, CBC and venous gas analysis;

8) IMP dispensation;

9) IMP reconciliation (Subjects must return any unused IMP).

9.1.4 Treatment Period

Assessment at each on-treatment visit will include:

1) Perform physical examination, including post-void body weight and height;

2) Record medical/PKD history;

3) Record concomitant medications and ensure subject's treatment meets current standard of care including lifestyle and dietary recommendations, especially for ingestion of at least2-3 liters of fluid per day as appropriate, unless otherwise directed by study doctor;

4) Assess AEs, if reported;

5) Assess vital signs (include heart rate and blood pressure);

6) Serum pregnancy test for WOCBP;

7) Collect urine and blood samples for clinical laboratory analyses, including serum creatinine, liver function tests, glucose metabolism parameter, CBC and venous gas analysis;

8) IMP dispensation;

9) IMP reconciliation (subjects must return any unused IMP);

10) Non contrast enhanced CT-scan of the kidneys for TKV measurement (at the end of month 24).

9.1.5 Follow-up Period

Assessments at each follow-up visit will include:

1) Perform physical examination, including post-void body weight and height;

2) Record medical/PKD history;

 Record concomitant medications and ensure subject's treatment meets current standard of care including lifestyle and dietary recommendations, especially for ingestion of at least
 2-3 liters of fluid per day as appropriate, unless otherwise directed by study doctor;

4) Assess AEs, if reported;

5) Assess vital signs (include heart rate and blood pressure);

6) Serum pregnancy test for WOCBP (second visit);

7) Collect urine and blood samples for clinical laboratory analyses, including serum creatinine, liver function tests, glucose metabolism parameter, CBC and venous gas analysis (second visit).

The above follow-up assessments will also be performed for a subject who interrupts IMP for more than 10 days, in order to collect their data in the event that they never restart IMP treatment.

9.1.6 Efficacy Assessments

9.1.6.1 Serum Creatinine for Estimated Glomerular Filtration Rate

The serum creatinine concentration is related to eGFR and is commonly used to estimate renal function in clinical practice. Alteration in metabolism of creatinine and methodological interference in its measurements may impact accuracy of the serum creatinine and renal function estimation. Below are suggested measures to decrease serum creatinine variability prior to the monthly blood draws required by this protocol:

- Maintain a stable dietary protein intake and avoid very different or high cooked meat protein meals the day before each scheduled serum creatinine assessment;
- Maintain a stable exercise routine and avoid very different or heavy physical activity/exercise the day before each scheduled serum creatinine assessment;

- Maintain a stable water intake, aimed at avoiding thirst consistently throughout the trial recommended ingestion of at least 2-3 liters of fluid (including in solid, semi-solid, and liquid foods) per day, unless otherwise directed by your study doctor;
- Plan to arrive at the same time for each blood-draw and clinic visit to better standardize time of the sample collection throughout the trial;
- Avoid forbidden medications.

Serum creatinine is stable when stored frozen; therefore, blood sample will be analyzed by the laboratory as soon as it is received and accessioned.

Ongoing, analysis will be conducted for each subject upon his/her individual completion of all their assessments within the trial (not at the end of the trial).

The eGFR values will be calculated from the laboratory serum creatinine concentrations taken at screening and during every trial visit. In the screening period, the first two assessments must be used to determine the eGFR values that will be averaged for determination of meeting inclusion criteria.

